5.8 Subject Questionnaire and Other Information

After all subject testing has been completed, the study participants will be provided a sample meter that displays a hypoglycemia/hyperglycemia reading. Following this, they are asked to complete a usability questionnaire. The trained study staff will administer a questionnaire to the subjects and check for completeness of the subject's responses. In the event of a physical, visual or neurological impairment that makes it difficult for a subject to complete the questionnaire, a subjects' verbal responses will be accepted and recorded.

5.8.1 Questionnaire: Evaluation of Instructions for Use – User’s Manual – Quick Reference Guide -ease of use of the system

The questionnaire will include statements for which a numerical score or rating will be provided by subjects (1=Very Difficult, 2=Fairly Difficult, 3= Neither Easy nor Difficult, 4=Fairly Easy, 5=Very Easy). The frequency distribution of the scores will be tabulated. In addition, the percent of subjects scoring 3 or more will be calculated for each statement along with exact 95% confidence intervals.

	Questions	Very Difficult	Fairly Difficult	Neither Easy nor Difficult	Fairly Easy	Very Easy
1	Understanding the overall instructions in the User’s manual and Quick reference guide is...	1	2	3	4	5
2	Following the instructions in the User’s manual on how to run a blood sugar and ketone test is...	1	2	3	4	5
3	Performing a blood test with this meter is...	1	2	3	4	5
4	Seeing and reading the meter display is...	1	2	3	4	5
5	Viewing my blood sugar and ketone test results on the meter is...	1	2	3	4	5
6	Handling the meter is...	1	2	3	4	5
7	Handling the test strips is...	1	2	3	4	5
8	Following the instructions on how to insert a test strip in the meter is...	1	2	3	4	5
9	Understanding the indicator of hypoglycemia/hyperglycemia is ...	1	2	3	4	5

	Method Comparison/User Evaluation of the i-SENS Self-Monitoring Blood Glucose / β-Ketone System(CareSens PRO GK BT)	Document No. BGM-2205084
	Authorized approval of controlled documents is required for external release.  Controlled Document  Uncontrolled Document	Version No. 2

						
10	Understanding the error message displayed on the meter screen is...	1	2	3	4	5
11	Changing the test mode from blood sugar to ketone is...	1	2	3	4	5
12	Recognizing that the test mode has changed is...	1	2	3	4	5

Note 1 – If the subject does not experience an error message during his/her testing, an error message (e.g. Er1 – A used test strip was inserted) will be demonstrated by the trained study staff after the subject completes all fingerstick testing

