Note: The meter automatically recognizes the measuring strip when each strip is inserted. If the KetoSens strip is inserted, KETONE will appear on the result window.

5) Immediately within 5 minutes of the first evaluable meter reading, the trained study staff collects more blood for Rx Imola measurement (approx. 500~550 μ L) using a Tenderlett TM or tenderlett-like single use lancing device. A total of up to 3 additional lancings are allowed to collect blood in the collection tubes. Centrifuge blood within 10 minutes from sample collection and conduct Rx Imola measurements within 20 minutes of centrifugation. Maximum of 35 minutes to complete from evaluable meter result.

6) Collect more blood and fill two micro hematocrit tubes for hematocrit test. The blood for hematocrit test can be taken from one of fingersticks already done.

Note: The subject's hematocrit measurement should be within 20-60% in order for the result to be considered evaluable.

7) For any occurrence of meter errors, the subject should follow the instructions in the user's manual.

8) The time of each test, meter results, any occurrence of meter error codes is recorded by the trained study staff on CRF.

9) Each evaluable fingerstick meter results are compared to the capillary YSI results and Rx Imola results. (More than one comparator measurement results averaged for each sample)

NOTE: If plasma cannot be measured immediately using YSI and Rx Imola within 15 mins after blood collection (in case of analyzer correction or device malfunction), store the plasma separated from the blood collection tube refrigerated.

For the study, multiple meters will be used and strips of at least 10 vials/packages over at least 3 lots will be used and rotated.

Table 1. Blood Testing Schematic

Fingerstick testing	

 • Select strips for subject blood testing (Lot A, Lot B and Lot C rotated) • Record time of 1st test 	
Glucose First lancing	
	Subject test
	
 • Study Staff records time of test, result of glucose and if subject completed each step properly (check boxes on CRF), and if subject encountered any problems.
Tenderlett or similar (Study Staff) stick	
	For YSI testing

 • Immediately following meter test (\leq5 minutes), study staff lances subject fingertip • Record time of lancing • Collect blood in Sodium Heparin tube (approx. 300-350 μL) 	

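### The only questionnaire percentage with a confidence interval groups neutral answers with easy ones, and items 2, 3 and 5 do not let ketone ratings be separated from glucose

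*Combined protocol and SAP*

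**What the plan says.** Section 5.8.1 of the combined protocol and SAP applies one five-point scale to all 12 statements: "1=Very Difficult, 2=Fairly Difficult, 3= Neither Easy nor Difficult, 4=Fairly Easy, 5=Very Easy". Two summaries follow. The first is that "The frequency distribution of the scores will be tabulated". The second, introduced as an addition, is that "the percent of subjects scoring 3 or more will be calculated for each statement along with exact 95% confidence intervals". No other percentage or interval is planned for the questionnaire. Sections 5.8.2 and 10 add only descriptive statistics and, where suitable, histograms.

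The items at issue are:

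- Item 2: "Following the instructions in the User’s manual on how to run a blood sugar and ketone test is"
- Item 3: "Performing a blood test with this meter is"
- Item 5: "Viewing my blood sugar and ketone test results on the meter is"
- Item 11: "Changing the test mode from blood sugar to ketone is"

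The note in Section 5.4 says: "The meter automatically recognizes the measuring strip when each strip is inserted". It adds that the result window shows the ketone label once the ketone strip is in.

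Section 2 includes usability and an assessment of the labelling in the study's purpose, and its first objective covers both analytes. Section 9 sets acceptance criteria for glucose and ketone accuracy and none for usability.

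**The concern.** Section 5.8.1 is headed as an evaluation of the instructions and of how easy the system is to use. A reader will naturally take its one percentage with an interval as the share of users who found a step easy. Because the cut-point takes in the midpoint, the percentage answers a weaker question: how many did not call the step difficult.

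The item wording raises a separate problem. The device is a combined glucose and ketone system, and Section 1 describes two kinds of strip with different blood volumes (0.4 and 0.5 μL) and times to result (5 and 8 seconds). A user might rate the two tests differently. Where one rating covers both, or where the item does not say which test is meant, that difference is never recorded.

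The two problems differ in kind. The cut-point can be changed at any time from the collected scores. The merged ratings cannot be separated once subjects have completed the form.

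**Working it through.** **Inputs.** The scale, the cut-point and the item wording come from Section 5.8.1. The number 350 is the minimum number of evaluable subjects in Section 3. The documents give no expected questionnaire result, so there is no planned figure to reproduce. The shares answering 1–2 (2% to 10%) and 3 (0% to 40%) are assumptions chosen to show a range.

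**Cut-point.** Let d, m and e be the shares scoring 1–2, 3 and 4–5, with d + m + e = 1.

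- Planned summary: P(≥3) = m + e = 1 − d. It does not depend on m.
- Share finding the step easy: P(≥4) = e = 1 − d − m.
- Difference: P(≥3) − P(≥4) = m, exactly the neutral share.

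With n = 350 and d about 5% (18 subjects), P(≥3) = (350 − 18)/350 = 332/350 = 94.9%, exact (Clopper–Pearson) 95% CI 92.0 to 96.9. Subtracting the neutral answers gives:

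| Assumed neutral share | Neutral answers | Scoring 4 or 5 | Exact 95% CI |
|---|---|---|---|
| 0% | 0 | 332/350 = 94.9% | 92.0 to 96.9 |
| 5% | 18 | 314/350 = 89.7% | 86.0 to 92.7 |
| 10% | 35 | 297/350 = 84.9% | 80.7 to 88.4 |
| 20% | 70 | 262/350 = 74.9% | 70.0 to 79.3 |
| 40% | 140 | 192/350 = 54.9% | 49.5 to 60.2 |

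Varying d shifts both figures together. At 2% difficult the planned summary is 343/350 = 98.0%. At 10% it is 315/350 = 90.0%. At 20% neutral the corresponding 4–5 figures are 273/350 = 78.0% and 245/350 = 70.0%. In the limiting case where all 350 answer 3, the planned summary is 100% (exact 95% CI 99.0 to 100) although nobody rated the step easy. That case shows what the statistic measures; it is not a forecast.

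**Which ketone tasks get their own rating.**

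- Following the instructions: item 2 only, shared with glucose.
- Running the test: item 3 only, analyte not named.
- Viewing the result: item 5 only, shared with glucose.
- Handling and inserting strips: items 7 and 8, strip type not named.
- Understanding an alert: item 9 covers the hypoglycemia/hyperglycemia indicator only.
- Noticing that the mode has changed: item 12. This is a genuine user task and bears on the switch to ketone.
- Changing the mode: item 11. Under Section 5.4 the user inserts the ketone strip and the meter does the rest, so a score could refer to choosing the strip, inserting it or something else.

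No item therefore gives a ketone-only rating of following the instructions, running the test or viewing the result.

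**Other ketone evidence.** Section 5.4 and its Table 1 have staff record, for the ketone self-test, times, results, number of lances, step completion, problems and error codes. These are observations by staff, not ratings by users, and Section 10 names no summary of step completion or problems.

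**The case against.** The strongest reply is that the plan already shows what is needed. All five score categories are tabulated for every statement, so the neutral share is visible and the 4–5 percentage, with its interval, follows from the counts. The plan never calls a score of 3 or more favourable or easy; taken literally, the statistic is a coherent measure of not being difficult. There is no usability pass mark or hypothesis test. The gap could also be small: with 5% difficult and 5% neutral it is 18/350, about 5 points. All of this stands, and it confines the cut-point problem to how one descriptive figure is chosen and labelled.

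A reader might infer that the questionnaire as a whole overstates ease of use. The documents do not support that: the scores collected are the same under any cut-point, and the overstatement arises only if one summary is read as ease.

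A reader might also infer that the study cannot show ketone usability at all. That is too strong. Item 12 gives some information on the switch to ketone, staff records cover performance of the ketone test, and ketone accuracy in untrained hands is itself an objective. What is missing is narrower, namely separate user ratings of three ketone tasks. Tabulating the distribution does not supply them.

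On item 11, the user still has to choose and insert the ketone strip, and that is how the mode changes. Someone who struggled could score it low, so a claim that the item draws inflated scores would be speculation. The supportable point is that its wording does not match the procedure.

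**Conclusion.** The point holds as a low-cost improvement to a secondary, descriptive part of the study.

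- **Cut-point.** The one percentage with an interval measures the share not rating a step difficult and exceeds the share rating it easy by the neutral share. The identity is exact. Its size is unknown in advance: zero if nobody answers 3, and 10, 20 or 40 points at the neutral shares assumed above.
- **Items.** Items 2 and 5 each combine the two analytes and item 3 names neither, so user ratings of following the ketone instructions, running the ketone test and viewing its result cannot be recovered after collection. This is the more important part because it cannot be repaired later.
- **Item 11.** Its wording does not match the automatic strip recognition in Section 5.4.

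No accuracy result or acceptance decision changes. A reader should not infer that a usability pass would be wrongly declared, because Section 9 contains no usability criterion.

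**What to change.** 1. In Section 5.8.1, report for each statement the percentage scoring 4 or 5 with an exact 95% confidence interval. The percentage scoring 3 or more may stay beside it if labelled as not difficult.
2. Before enrolment, split items 2 and 5 into a glucose version and a ketone version, and do the same for item 3. Items 7 and 8 could name the strip type if space allows.
3. Reword item 11 around what the user does, which is selecting and inserting the ketone strip.

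The first change needs no new data and can be made at any time before reporting. The second adds three items to a 12-item form (15 in total) and cannot be made up for after subjects have answered. Section 8.2 requires sponsor and IRB approval for amendments, so both form changes are best made together. The drawback for the sponsor is that the new percentages will be less favourable for any statement with neutral answers.

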5.8.2 Demographic, Diabetes History, Hematocrit, and Subject Questionnaire

Descriptive statistics for demographics, diabetes history, and subject questionnaires will be calculated. Histograms will be constructed where appropriate.

Hematocrit will be measured in duplicates and averaged for each subject where available. The subject's hematocrit measurement should be within 20-60% in order for the subject to be considered evaluable and be used for blood glucose measurement comparisons. The mean, median, minimum, maximum, and standard deviation, will be computed for average hematocrit determinations.

5.8.3 Data Evaluability

Blood glucose/ β -ketone data will be considered not evaluable for the following reasons:

- Subjects without a hematocrit result or a hematocrit result outside of 20-60% range.
- The readings from the subject meter tests that the subject feels were incorrectly completed. (If the subject states that the test s/he performed was completed incorrectly, and repeats the test, then the new reading will be used as the subject's evaluable result.)
- Failure to lance the subject's fingertip using the Tenderlett device or Tenderlett-like device within 5 minutes of the subject's first fingerstick self- test.
- Failure to separate the plasma from the red blood cells within 10 minutes of Tenderlett blood collection.
- Failure to measure YSI/Rx Imola reading within 2 hours after separating plasma from the red blood cells.

	Method Comparison/User Evaluation of the i-SENS Self-Monitoring Blood Glucose / β-Ketone System(CareSens PRO GK BT)	Document No. BGM-2205084
	Authorized approval of controlled documents is required for external release.  Controlled Document  Uncontrolled Document	Version No. 2

6. Risk / Benefit Assessment

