5.4 Subject Evaluation Procedure

Each subject is provided with all the materials needed for blood glucose/ β -ketone self-testing.

- 1) The subjects are given sufficient time to review the user's manual and the quick reference guide. No training is provided by the trained study staff.

Note: The subjects should obtain their own fingertip capillary sample and perform a test using only the draft device labeling as instructions (user's manual and the quick reference guide). No other training or prompting should be provided to the subject and no assistance should be given from the trained study staff. The subjects should be sequestered in different stations that they cannot observe or be influenced by the testing technique of other subjects or trained study staff.

- 2) The subject washes his/her hands with warm water and soap, rinses and dries well.
- 3) The subject lances his/her finger using a lancing device and performs a blood glucose test with a glucose test strip on the meter. Three successful fingersticks/lances are allowed maximum (actual lances on the finger) to get a meter result. The lancet should be changed after each actual fingerstick. The trained study staff records the times of the meter tests, results, number of successful lances, and marks whether the subject completed all steps on the CRF.

	Method Comparison/User Evaluation of the i-SENS Self-Monitoring Blood Glucose / β-Ketone System(CareSens PRO GK BT)	Document No. BGM-2205084
	Authorized approval of controlled documents is required for external release.  Controlled Document  Uncontrolled Document	Version No. 2

4) Immediately within 5 minutes of the first evaluable meter reading, the trained study staff collects more blood for YSI and hematocrit measurement (approx. 300-350 μ L) using a Tenderlett TM or tenderlett-like single use lancing device. A total of up to 3 additional lancings are allowed to collect blood in the collection tubes. Centrifuge blood within 10 minutes of sample collection and conduct YSI within 20 minutes of centrifugation. Maximum of 35 minutes to complete from evaluable meter result. After measuring blood glucose, the subject lances his/her finger and performs a β -ketone test with a β -ketone test strip on the same meter. The trained study staff /technician records the times of the meter tests, results, number of successful lances, and marks whether the subject completed all steps on the CRF.

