	Method Comparison/User Evaluation of the i-SENS Self-Monitoring Blood Glucose / β-Ketone System(CareSens PRO GK BT)	Document No. BGM-2205084
	Authorized approval of controlled documents is required for external release.  Controlled Document  Uncontrolled Document	Version No. 2

 • Centrifuge blood and record time (should be within 10 minutes of sample collection) • Test the sample and record time and result of glucose on CRF 	
β-ketone Second lancing	Subject test

 • Study Staff records time of test, result of β-ketone and if subject completed each step properly, and if subject encountered any problems. 	
Tenderlett or similar (Study Staff) stick	For Rx Imola testing

 • Immediately following meter test (\leq5 minutes), study staff lances subject fingertip • Record time of lancing • Collect blood in Sodium Heparin tube (approx. 500 ~ 550μL) • Centrifuge blood and record time (should be within 10 minutes of sample collection) • Test the sample and record time and result of glucose on CRF 	
Hematocrit Testing	

 • Fill 2 micro hematocrit tubes and record time and result of hematocrit 	
Record meter reading or meter error codes or subject errors as appropriate	

Note: Trained study staff should use a new pair of gloves for each subject and should change gloves between subjects.

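### Section 5.8.3 times the 5-minute comparator lance from the first self-test and Section 5.4 from the first evaluable reading, so a pair that complies with 5.4 can be excluded when a subject repeats a test

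*Combined protocol and SAP*

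**What the plan says.** **Procedure (Section 5.4).** Step 4, for glucose: "Immediately within 5 minutes of the first evaluable meter reading, the trained study staff collects more blood for YSI and hematocrit measurement". Step 5, for β-ketone: "Immediately within 5 minutes of the first evaluable meter reading, the trained study staff collects more blood for Rx Imola measurement". Both start the clock at the first evaluable reading. Table 1 gives each analyte its own block. In each block the staff lance comes at most 5 minutes after the meter test ("Immediately following meter test"), but the table does not say whether a first or an evaluable test is meant.

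**Evaluability (Section 5.8.3).** The third bullet counts data as not evaluable if staff fail to lance the "fingertip using the Tenderlett device or Tenderlett-like device within 5 minutes of the subject's first fingerstick self- test". The bullet covers both analytes and does not say which self-test is meant for which comparator.

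**Repeats (Section 5.8.3).** The second bullet covers a subject who says that a test was completed incorrectly "and repeats the test, then the new reading will be used as the subject's evaluable result". Section 5.4 step 7 also sends subjects back to the user's manual after a meter error.

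**Role of the list.** Note 2 in Section 4.3 says that all evaluable data from eligible subjects are analysed, and refers to Section 5.8.3 for what is evaluable.

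**The concern.** One document gives two start points for the same 5-minute limit. They coincide when the first self-test is also the evaluable one, and separate when a test is repeated. Staff can then follow Section 5.4 exactly and produce a pair that Section 5.8.3 rejects.

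For a repeater, the 5.8.3 clock starts at a reading that is not compared with anything. It does not measure the interval that matters for a method comparison, which is the time between the paired meter reading and the comparator sample.

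The 5.8.3 list helps decide which pairs enter the X/Y counts in Tables 2 and 3, on which the Section 9 criteria are judged. The objective in Section 2 is whether untrained people can obtain acceptable results, and people who repeat a test are part of that population. With both rules in the text, two analysts could classify the same pair differently, and the choice could be made after the results are known.

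**Working it through.** **Inputs.** The 5-minute limit and its start at the first evaluable reading come from 5.4 steps 4 and 5. The same limit, started at the first self-test, comes from 5.8.3 bullet 3. That the evaluable reading may be a later one comes from 5.8.3 bullet 2. The plan states no figure of its own that could be reproduced here.

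**Set-up, for one analyte.** Put the first self-test at minute 0, the evaluable reading at minute r, and the staff lance d minutes after that reading, with d ≥ 0.

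- Section 5.4 requires d ≤ 5.
- Section 5.8.3 requires r + d ≤ 5, that is, d ≤ 5 − r.

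The rules are the same only at r = 0. For r > 0, any lance with d above 5 − r but no more than 5 complies with 5.4 and fails 5.8.3. The disagreement runs one way: since r ≥ 0, every pair that meets 5.8.3 also meets 5.4.

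| r (min) | Latest lance under 5.4, minutes after evaluable reading | Latest lance under 5.8.3, minutes after evaluable reading |
|---|---|---|
| 0 | 5 | 5 |
| 1 | 5 | 4 |
| 2 | 5 | 3 |
| 3 | 5 | 2 |
| 4 | 5 | 1 |
| 5 | 5 | 0 |

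Beyond r = 5, no lance made after the evaluable reading can satisfy 5.8.3.

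**Example.** With r = 4 and d = 4, the 5.4 gap is 4 ≤ 5, which complies. The 5.8.3 gap is 4 + 4 = 8 > 5, which excludes the pair.

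**What the table does not show.** These are limits on time, not shares of pairs. Turning them into a number of lost pairs would need the repeat rate, the distribution of r and the distribution of d. The documents give none of these. At r = 3, for instance, no pair is lost if staff lance within 2 minutes of the evaluable reading.

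**Hypothetical sensitivity of the glucose verdict.** Apply the 99% criterion without rounding (the plan states no rounding rule).

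- At the minimum of 350 pairs, 0.99 × 350 = 346.5, so 347 must lie within ±20% and 3 may lie outside.
- At 351 pairs, 0.99 × 351 = 347.49, so 348 must lie within.
- With 351 pairs and 4 outside, 347/351 = 98.9%, which fails.
- If one of those 4 is excluded, 347/350 = 99.1%, which passes, and the 350 minimum is still met.

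This is a constructed case. It would hold for the exclusion of one failing pair for any reason, so it shows only how little slack the criterion has.

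**The case against.** **A harmonising reading.** Bullet 2 of 5.8.3 replaces the faulty reading with the new one. Bullet 3 could therefore be read as meaning the first valid self-test, in line with 5.4. This is plausible as intent, but no passage says so. Section 5.4 uses the word evaluable and 5.8.3 omits it, directly after a bullet that separates a discarded test from an evaluable one.

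**A deliberately tighter rule.** The sponsor might have wanted a stricter limit for the analysis. For a repeater, however, the stricter limit is timed from a reading that does not enter the comparison, so it does not control the gap between the paired samples.

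**Few pairs, and visible ones.** Section 5.4 and Table 1 ask for the lance immediately, the meter reads in 5 or 8 seconds, and Section 10 requires unused data to be noted with reasons. All of this stands. It limits the likely size and makes exclusions traceable, but it does not settle which rule applies.

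**The three-lance allowance.** Section 5.4 step 3 says "Three successful fingersticks/lances are allowed maximum (actual lances on the finger) to get a meter result". A reader might infer that every extra lance opens a gap between the clocks. The wording describes several lances towards one meter result, so it gives only weak support. The clear cases are the repeat under 5.8.3 bullet 2 and, possibly, a repeat after a meter error.

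**Stronger readings that the documents do not support.**

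- A reader might infer that bullet 3 removes only repeaters. It also excludes a non-repeater who is lanced late. Only the pairs on which the two clocks disagree are confined to repeaters.
- A reader might infer that β-ketone pairs fail even without a repeat, because the glucose self-test comes first. Bullet 3 does not rule this out in words, but the step order and the separate β-ketone block in Table 1 point to one clock per analyte.
- A reader might infer that exclusions flatter the device. The rule depends on timing and not on agreement with the comparator, and nothing in the documents shows how accuracy relates to repeating a test.

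**Conclusion.** The conflict is real as written. For a subject whose evaluable reading is a repeat, Section 5.8.3 can exclude a pair that Section 5.4 accepts, because it times the lance from a reading that is not compared. This should be fixed before data are classified.

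Confidence is high on the textual conflict and low on its consequence. The number of pairs affected cannot be computed and may be zero, and the direction of any bias is unknown. A change in the glucose verdict is arithmetically possible at the margin but hypothetical.

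The conclusion assumes that the clock is read per analyte, that 5.8.3 is applied as worded, and that staff lance after the evaluable reading, as 5.4 directs.

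**What to change.** Reconcile the two sections by rewording the third bullet of 5.8.3 so that the limit reads: *within 5 minutes of the evaluable meter reading being compared (the glucose reading for YSI, the β-ketone reading for Rx Imola)*. This matches 5.4 and makes explicit the separate clock for each analyte that Table 1 implies. Making the first self-test the common start in both sections would also end the contradiction. It is the weaker choice, because it does not measure the interval between the paired samples and leaves a repeater only 5 − r minutes.

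Within the unused-data reporting already planned in Section 10, give the number of pairs excluded under this bullet for each analyte, separating subjects who repeated a test from those who did not. A single total would mix late lances in non-repeaters with the cases at issue here.

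The cost is one bullet of wording and two counts per analyte. No new data are needed. Under 5.4 step 3, "The trained study staff records the times of the meter tests, results, number of successful lances" are already captured, and Table 1 tells staff "Record time of lancing" for each comparator stick.
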